11.2 Primary Performance Endpoint

FWCS scores will be summarized per subject and time point. Changes from baseline to the last follow-up visit will be summarized as well. For analyzing the changes over time within each arm, the Repeated

measures or Friedman paired test followed by Dunn's post hoc test (as appropriate based on Shapiro and Wilk test for normality) will be applied. For comparison between devices two-sample T-test or Non-parametric, Mann-Whitney Rank sum test (as is appropriate) will be applied.

In addition, in order to keep the study's power, data of the two sites will be pooled together and an Analysis of Covariance (ANCOVA) model will be applied for analyzing the primary endpoint, with adjustment to suspected confounders (baseline measure and site).

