The following assessment method will be applied by the blinded assessors (by images only):

- FWCS - Fitzpatrick Wrinkle Classification System

2.4.Secondary Outcome Endpoints

The following criteria will be assessed as secondary outcome endpoints:

- Secondary Effectiveness/Performance shall be assessed and quantified by a handling physician (one of the team's investigators of the study).

The following assessment methods will be applied (frontal clinical assessment or by images):

- FWCS - Fitzpatrick Wrinkle Classification System
- GAIS - Global Aesthetic Improvement Scale Assessment
- WAS - 5-point Wrinkle Assessment Scale
- Subject Experience
- Pain Level VAS Scale
- Subject Subjective Downtime Assessment

- Subject redness, edema and crust assessment (time for resolution)
- End-User Experience Assessment

Clinic Visits Baseline, 4wk, 8wk, (optional 12wk and 16wk), 20wk, 28wk, 42wk

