10. SAMPLE SIZE CONSIDERATIONS

The rationale for sample size calculation was based on difference between treatments arms in the improvement post treatment in FWCS scores.

$$\text{Improvement} = FWCS_{6 \text{ months}} - FWCS_{Baseline}$$

$$\text{NIM} = Improvement_{Tixel} - Improvement_{Laser} \geq -0.5$$

The assumption that Tixel is non inferior as compared to Laser in the effectiveness as evaluated by FWCS 6 months after first treatment.

FWCS ranges from fine to deep wrinkles in a 1 to 9 scale.

Previous studies demonstrated that the standard deviation of the change in FWCS post 6 months is 0.75.

Assuming that the non-inferiority margin is $\text{NIM} \geq -0.5$, and the $SD = 0.8$ a sample size of 32 completers per group will enable to conclude that Tixel is non inferior to ResuFx with 95% confidence and with 80% power.

Taking into account a dropout rate of 20% a total of 40 cases per group should be recruited. To allow for the possibility of a higher dropout rate a total of 41 cases per group will be recruited.

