11. STATISTICAL METHODS

11.1 General

All measured variables and derived parameters will be listed individually and, if appropriate, tabulated by descriptive statistics.

For categorical variables summary tables will be provided giving counts and percentages.

For continuous variables summary tables will be provided giving count, arithmetic mean, standard deviation, median, 25th and 75th percentile, minimum and maximum of variables by device.

All tests will be two-tailed, and a p-value of 5% or less will be considered statistically significant.

The data will be analyzed using the SPSS version 925.0.

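### Section 10 sizes the trial for non-inferiority with a 0.5-point FWCS margin, but Section 11 gives the primary comparison no margin, confidence bound or decision rule

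*Combined protocol and SAP*

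**What the plan says.** Section 10 is the only place that states a hypothesis. It sets a non-inferiority margin of 0.5 points on the difference between arms in FWCS change and assumes an SD of 0.8. It says that 32 completers per group "will enable to conclude that Tixel is non inferior to ResuFx with 95% confidence and with 80% power". It defines improvement as the 6-month score minus the baseline score and requires Tixel minus laser to be at least −0.5. On the scale it says: "FWCS ranges from fine to deep wrinkles in a 1 to 9 scale". It places the assessment "as evaluated by FWCS 6 months after first treatment".

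Section 11.1 sets the general rule: "All tests will be two-tailed, and a p-value of 5% or less will be considered statistically significant". Section 11.2, on the primary endpoint, says: "Changes from baseline to the last follow-up visit will be summarized as well". For the devices it says: "For comparison between devices two-sample T-test or Non-parametric, Mann-Whitney Rank sum test (as is appropriate) will be applied". It then adds that the two sites will be pooled and "an Analysis of Covariance (ANCOVA) model will be applied for analyzing the primary endpoint", adjusted for baseline and site.

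Section 11 does not mention non-inferiority, the margin, a confidence interval or a success criterion.

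**The concern.** The methods in Section 11.2, used under the Section 11.1 rule, test whether the devices differ. Neither outcome answers the Section 10 question. A p-value above 0.05 does not exclude a 0.5-point deficit, and one below 0.05 does not show on which side of the margin the difference lies. A Mann-Whitney p-value cannot be compared with a margin on a mean difference at all. The ANCOVA could supply the required estimate and interval, but the plan neither asks for the interval nor says that the ANCOVA decides.

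Section 10 cannot fill the gap unaltered, because three inputs to a decision rule conflict:

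- **Level.** The sample size matches a one-sided 5% test, while Section 11.1 prescribes two-tailed 5%.
- **Sign.** Follow-up minus baseline is negative for a benefit, so a lower limit of −0.5 on Tixel minus laser points the wrong way.
- **Time.** Section 10 counts six months from the first treatment; Section 11.2 uses the last follow-up visit.

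With these open, what counts as success could be settled after the data are seen.

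**Working it through.** **Inputs.** From Section 10: margin 0.5, SD 0.8, 32 completers per group, 80% power, 20% dropout, 41 recruited per group. From Section 11.1: two-tailed 5%. Assumed, because the documents do not state it: true difference 0. Also assumed: equal SD in both arms and, unless noted, no gain from covariate adjustment.

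**1. Reproducing the sample size.** n per arm = 2 × SD² × (z_α + z_0.80)² / margin².

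- One-sided 5%: 2 × 0.64 × (1.6449 + 0.8416)² / 0.25 = 31.65, so 32. After dropout, 32 / 0.8 = 40. Both match Section 10.
- One-sided 2.5%, the level of a two-sided 95% interval: 2 × 0.64 × (1.9600 + 0.8416)² / 0.25 = 40.19, so 41. This does not match.

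With a true difference of 0, the plan's figure therefore rests on one-sided 5%.

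**2. Power with 32 completers.** The standard error is 0.8 × √(2/32) = 0.20, so the margin is 0.5 / 0.20 = 2.5 standard errors away.

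| Rule | Power, t | Power, normal | Smallest n for 80%, t |
|---|---|---|---|
| One-sided 95% bound | 79.6% | 80.4% | 33 |
| Two-sided 95% CI | 69.2% | 70.5% | 42 |

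**3. Non-significance is not non-inferiority.** With 62 degrees of freedom and an observed SD of 0.8, p > 0.05 means an observed difference within ±1.999 × 0.20 = ±0.400. Excluding a 0.5 deficit with a one-sided 95% bound needs an observed deficit below 0.5 − 0.334 = 0.166. With a two-sided 95% CI it needs one below 0.5 − 0.400 = 0.100. Observed deficits between those limits and 0.400 are non-significant yet leave the margin unexcluded. In 400,000 simulated trials with a true difference of 0, this happened in 17.7% (one-sided 95% bound) and 28.2% (two-sided 95% CI).

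**4. If p > 0.05 were read as non-inferior.** With Tixel truly 0.5 worse, the noncentral t distribution gives P(p > 0.05) = 0.308 at 32 per arm and 0.202 at 41 per arm. A correct rule allows 5% (one-sided, as the sizing implies) or 2.5%.

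**5. The sign.** Higher scores mean deeper wrinkles, so a benefit is a negative change.

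- Tixel change 0, laser change −1: difference 0 − (−1) = +1. This satisfies ≥ −0.5 although Tixel did worse.
- Tixel change −2, laser change −1: difference −2 − (−1) = −1. This fails although Tixel did better.

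Applied literally with a one-sided 95% bound at 32 per arm, a Tixel truly worse by 0.5 would pass more than 99.9% of the time.

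**6. The time point.** The visit line in Section 2.4 reads "Clinic Visits Baseline, 4wk, 8wk, (optional 12wk and 16wk), 20wk, 28wk, 42wk", and the Section 9 flowchart labels the week-42 visit as the 6-month follow-up. The fifth treatment is at week 16, and 42 − 16 = 26 weeks, so the label counts from the last treatment. Even the flowchart's shortest course puts this visit at 32 weeks minus 29 days, about week 28. It is also the only post-baseline visit marked for blinded FWCS.

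**The case against.** The strongest reply is that Sections 10 and 11 belong to one document. Section 10 fixes the endpoint, the margin, 95% confidence and an inequality. Section 11.1 gives a level. The t-test and the ANCOVA both estimate a mean difference from which a bound follows directly. On this reading only a link is missing, the wording makes the intended direction obvious, and the flowchart's 6-month label lets both sections mean the same visit.

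Part of this stands. Section 11 is not silent on level, the sign may be a drafting slip, and the timing conflict comes down to the phrase about the first treatment. But the missing link is the decision rule itself. It cannot be inferred when the level in Section 11.1 differs from the one behind the sample size and the only printed criterion runs backwards.

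Four further points are fair:

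- The match to one-sided 5% depends on a true difference of 0. A true Tixel advantage of about 0.065 would also give 32 at one-sided 2.5%: 2 × 0.64 × (1.9600 + 0.8416)² / 0.565² = 31.5. Section 10 states no such advantage.
- The 18% and 28% are mostly ordinary lack of power. Under a correct rule 20.4% and 30.8% of trials of equal devices would fail anyway. They become errors only if p > 0.05 is taken as success, and the 31% and 20% rest on that same misreading, which no section adopts.
- If all 41 per arm complete, power with a two-sided 95% CI is already 79.8%.
- The plan also lacks a rule for combining the three blinded assessors' scores and an efficacy analysis set. Both need settling, but they are separate from this point.

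**Conclusion.** The concern holds and must be fixed. Followed exactly, the plan yields a two-tailed test of difference that cannot support the conclusion the trial was sized for, and the one criterion it prints accepts an inferior Tixel. No passage says that p > 0.05 will be read as non-inferiority, but Section 11 supplies no other rule. That misreading would raise the false-pass rate at a true 0.5 deficit from 5% or 2.5% to 31% with 32 per arm, or 20% with 41 per arm. These figures assume SD 0.8 in both arms and an unadjusted t analysis. The power figures also assume a true difference of 0. The mismatch between Section 10 and Section 11, and the reversed sign, depend on none of these assumptions.

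**What to change.** In Section 11.2:

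- Make the planned ANCOVA on pooled sites the single primary analysis: change in blinded-assessor FWCS on treatment, baseline FWCS and site.
- Report the adjusted Tixel-minus-laser difference in change (follow-up minus baseline) with its confidence interval, and conclude non-inferiority only if the upper bound is below +0.5.
- Make the t-test and Mann-Whitney test sensitivity analyses.
- State the confidence level and match it to Section 10.

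In Section 10, correct the sign. In both sections name one time point, and reconcile the six months from first treatment with Visit 8.

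Cost depends on the level chosen:

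- **One-sided 95% bound (two-sided 90% CI).** Wording in Sections 10 and 11.2 only; 32 completers and about 80% power stand.
- **Two-sided 95% CI.** Restate power as about 69% at 32 completers, before any ANCOVA gain. Restoring 80% needs 42 completers, or 42 / 0.8 = 52.5, so 53 recruited per arm against 41 planned. Alternatively, covariate adjustment could supply the gain. With residual SD 0.8 × √(1 − r²), where r is the baseline-change correlation, power at 32 is 73.2% for r = 0.3, 80.1% for r = 0.48 and 86.7% for r = 0.6. The documents give no value for r, so it would have to be justified.

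Either way, the sponsor commits to one decisive analysis before the treatment comparison is seen.

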technology that has been designed to provide a comparable clinical effect as a pulsed laser, which can be used as a treatment modality for a variety of applications, including fractional treatment of human skin. The Tixel technology is based on the supply of contact-transferred heat from a high temperature (385°- 400°C) metal element (called a “tip”) consisting of an array of miniature pyramids. The tip creates a thermal effect in the tissue (usually 200-300 microns deep) in the tissue within 5 – 16 milliseconds, thus mimicking the pulsed laser action. The tip thermally generates a matrix of coagulation sites (or “micropores”) on the skin. Dermal heating and coagulative effect that occur during the treatment session provide for dermal remodeling and collagen restructuring that promote wrinkle reduction and general wrinkle appearance improvement.

Protocol Number:

CLN 0460

Study Design:

Prospective, single-blinded, randomized, controlled study

Number of Study Sites:

2

Study Population:

Male and female subjects between 40-70 years of age (inclusive) diagnosed with clinically evident periorbital wrinkles

Study Treatment:

Subjects will be treated with the Tixel for periorbital wrinkles every 4-6 weeks for a series of 3 to 5 treatment sessions followed by 3 follow up sessions (see flowchart for full schedule details and options). The number of treatments may vary from subject to subject and shall be determined by the investigators' assessment of the subjects' improvement.

The minimal estimation for study duration per subject is 27 weeks, and the maximal estimation is 47 weeks (please see study flowchart for further details).

Comparator Treatment:

The ResurFX Non-Ablative Laser with the M22 device by Lumenis (1565 nm) for treatment of periorbital wrinkles

2. STUDY OBJECTIVES:

To demonstrate the safety and performance of the Tixel fractional system for treatment of periorbital wrinkles in comparison to the selected market-cleared comparator.

2.1.Primary Outcome Endpoints:

Each subject shall be assessed based on FWCS. Each subject shall contribute two separate data time points to the study.

2.2.Safety

Physical and dermatological examinations, erythema, and adverse events (such as PIH, burns, etc.) monitoring will be performed and assessed at every visit (including follow up visits).

2.3.Effectiveness/Performance

Effectiveness/Performance shall be assessed and quantified by 3 blinded assessors.

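### Section 11.2 does not say which of a t-test, a Mann-Whitney test or an ANCOVA decides the primary device comparison, and the rank test does not estimate the mean difference to which the 0.5 margin applies

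*Combined protocol and SAP*

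**What the plan says.** Section 10 bases the sample size on the "difference between treatments arms in the improvement post treatment in FWCS scores" at six months. It uses a margin of -0.5, an SD of 0.8 (0.75 in previous studies) and 32 completers per group. This is a comparison of means.

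Section 11.2 then gives three routes to the device comparison:

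- A choice of two tests: "For comparison between devices two-sample T-test or Non-parametric, Mann-Whitney Rank sum test (as is appropriate) will be applied". Nothing defines what makes one of them appropriate.
- A third analysis, introduced by "In addition, in order to keep the study's power, data of the two sites will be pooled together": "an Analysis of Covariance (ANCOVA) model will be applied for analyzing the primary endpoint, with adjustment to suspected confounders (baseline measure and site", in parentheses that close there. It is an extra analysis and is not named as the deciding one.
- A normality check, "as appropriate based on Shapiro and Wilk test for normality", which stands in the preceding sentence. That sentence concerns change over time within each arm (repeated measures or Friedman).

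No test or interval in section 11 is tied to the -0.5 margin. Section 2.3 says "Effectiveness/Performance shall be assessed and quantified by 3 blinded assessors", but no rule for combining the three scores is given.

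**The concern.** Non-inferiority is a statement about one quantity against one margin. Here the quantity is a difference in mean change and the margin is half a point. A t-test or an ANCOVA estimates that quantity. A Mann-Whitney test asks which arm tends to rank higher. The two questions agree when the arms differ only by a shift, but can disagree when they differ in shape, for example if a minority respond strongly to one device.

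Because the deciding analysis is not named, it can be settled after the data are seen, and one of the candidates does not address the margin. If the three analyses disagree, the plan gives no way to say what the trial has shown.

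**Working it through.** **1. Reproduce the plan's sample size.** Inputs from section 10: margin 0.5, SD 0.8, power 80%, true difference 0.

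n per group = 2 × (z_α + z_β)² × SD² / margin²

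- One-sided 0.05: 2 × (1.645 + 0.842)² × 0.64 / 0.25 = 31.7, so 32. With 20% dropout, 32 / 0.8 = 40. Both match the plan.
- One-sided 0.025: 41, and 52 with dropout. This does not match.

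The planned number is therefore a comparison of means at one-sided 0.05.

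**2. Would a normality check steer towards the rank test, if one were used here?** This is simulated with 32 per arm, SD about 0.8 and a normal underlying change. Whole-point scoring, the combining rule and rater agreement are assumptions. The table gives the chance that Shapiro-Wilk rejects at 5% in at least one arm.

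| Subject score | Rejects |
|---|---|
| Continuous | 10% |
| Mean of three whole-point scores | 28% to 58% |
| Half-point score | 64% |
| Single or median whole-point score | about 100% |

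**3. The rank test under a pure shift.** Subtract the margin, then apply a one-sided 5% Mann-Whitney test (32 per arm, 3000 replicates). With a true deficit of 0.5 it declares non-inferiority in 4.6% to 5.8% of trials. With no true difference its power is 76% to 79%. Both are close to plan.

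**4. The rank test when the arms differ in shape.** Assumed improvements, with larger meaning better:

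- Laser 0/1/2/3 in 40/45/7/8%: mean 0.45 + 0.14 + 0.24 = 0.83; variance 1.45 - 0.83² = 0.761.
- Tixel 0/1/2 in 70/27/3%: mean 0.27 + 0.06 = 0.33; variance 0.39 - 0.33² = 0.281.
- Mean deficit 0.83 - 0.33 = 0.50, exactly the margin. Pooled SD = √((0.761 + 0.281)/2) = 0.72.

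Declaring non-inferiority here is an error. After adding 0.5 to Tixel, the chance that a Tixel subject outranks a laser subject is P(Tixel ≥ laser) = 0.70 × 0.40 + 0.27 × 0.85 + 0.03 × 0.92 = 0.537. The rank test's null value is 0.5, so it sees Tixel as better than the margin although the mean deficit equals the margin.

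Simulated at one-sided 5%, 32 per arm:

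| Version of the example | t-test | Margin-shifted Mann-Whitney |
|---|---|---|
| As above | 6% | about 15% |
| With reader error averaged over three readers (-1/0/+1 at 15/70/15%) | 6% | 11% |

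**5. The rank test as the plan words it.** Section 11.1 makes all tests two-tailed at 5%, and no margin enters. With a shift of the full 0.5 in a normal underlying change, an ordinary Mann-Whitney test gives p > 0.05 in 33% to 34% of trials. As a check, the t-test analogue has 0.5 / (0.8 × √(2/32)) = 2.5, so it is non-significant with probability P(Z < 1.96 - 2.5), about 29%. A non-significant result from either test does not show non-inferiority.

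**The case against.** Four points count against a stronger reading.

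- **A reader might infer that Shapiro-Wilk selects the between-device test.** The text does not say so. The check is attached to the within-arm sentence, and the device comparison has no stated criterion. The rejection rates in step 2 apply only if the check is carried over. This stands, although a choice with no rule is no more constrained than one with a poor rule.
- **A reader might infer that the rank test replaces the mean comparison.** It does not. The ANCOVA is planned whatever the normality result and adjusts for baseline and site. This stands. What remains is that the ANCOVA is not named as deciding.
- **A reader might infer a gross loss of error control.** A stronger skew (laser 0/1/2/4 in 50/30/10/10%, Tixel 0/1/2 in 65/30/5%) gives 49% for the shifted rank test against 7% for the t-test. Its pooled SD is 0.96, above the plan's 0.8. Shifting whole-point data by half a point also turns every tied pair (42% of pairs) into a Tixel win. It is not a fair headline.
- **The margin-shifted Mann-Whitney is not in the plan.** Steps 3 and 4 show what the rank route would do if it were linked to the margin. Nor does the plan say that success on any one of the three analyses is enough, so I attach no multiplicity figure.

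**Conclusion.** The point holds as a gap in the primary analysis: three candidate analyses, none named as deciding, and one that does not estimate the mean difference behind the margin and the sample size. It should be fixed. It is not fatal, because a suitable mean-based model is already planned.

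The size depends on the data. Under a pure shift the choice makes little difference to a margin-shifted rank test. With the assumed mild skew, at an SD close to the plan's, false non-inferiority is about 11% to 15% against 6% for the t-test. Those figures rest on assumed response distributions, whole-point scoring and 32 completers per arm. The one-third figure for the ordinary two-tailed rank test rests on a normal underlying change with SD about 0.8.

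The mismatch between one-sided 0.05 in the sample size and two-tailed 5% in section 11.1 is a separate matter and does not come from the choice of test.

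**What to change.** In section 11.2:

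- Delete the choice between t-test and Mann-Whitney for the primary between-device comparison.
- Make the planned ANCOVA (device, baseline, site) the single deciding analysis, applied to the mean of the three blinded assessors' scores.
- Compare the confidence bound for the adjusted mean difference with the 0.5 margin, and state a robust or bootstrap standard error for use if residuals are non-normal.
- Keep Mann-Whitney as a labelled sensitivity analysis that cannot change the conclusion.

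The sample size stays at 32 completers and 40 recruited per group at one-sided 0.05 (41 are planned). If the bound is instead taken from a two-sided 95% interval, the formula in step 1 asks for 41 completers and 52 recruited per group, and 32 completers give about 70% power; that follows from sidedness, not from this change. The cost is wording in the analysis section, and the sponsor gives up choosing the test after seeing the data.

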11.2.1 Safety Assessment

Frequency and incidence of physical and dermatological examinations will be summarized.

Adverse events will be reported in tabulated format based on all ITT (intent to treat data set).

11.3 Secondary endpoints

All parameters below will be summarized at baseline condition and all post-baseline conditions. The change from baseline to the last follow-up will be analyzed using Wilcoxon paired test.

The following secondary endpoints will be summarized in appropriate tables by device and visit:

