9. STUDY FLOWCHART AND FOLLOW-UP ASSESSMENTS

Procedure	Visit 1	Visit 2	Visit 3	Visit 4	Visit 5	Visit 6	Visit 7	Visit 8
	Treatment 1 ^c	Treatment 2	Treatment 3	Treatment 4 Optional	Treatment 5 Optional	1 month Follow-up 1	3 months Follow-up 2	6 months Follow-up 3
	T ₀ ^f (± 5d) ± Δ ^{ef}	T ₀ + 4w (± 5d) ± Δ	T ₀ + 8w (± 5d) ± Δ	T ₀ + 12w (± 5d) ± Δ ^e	T ₀ + 16w (± 5d) ± Δ ^e	T ₀ + 20w (± 8d) ± Δ ^e	T ₀ + 28w (± 8d) ± Δ ^e	T ₀ + 42w (± 8d) ± Δ ^e
Max duration	-	4w+5d	8w+10d	12w+15d	16w+20d	20w+25d	28w+33d	40w+41d ~ 47w
Min duration	-	4w-5d	8w-10d	-	-	12w-15d	20w-23d	32w-29d ~28w
Subject Screening, Enrolment Procedure & Informed Consent ^g , Post treatment care instructions	X							
Facial dermatological skin examination	X	X	X	X	X	X	X	X
Inclusion/ Exclusion criteria	X							
Medical/Surgical history	X							
Demographics	X							
Limited Physical examination ^a	X							
Concomitant Therapy/Medication	X _b	X	X	X	X	X	X	X
Verbal Inquiry regarding pregnancy	X	X	X	X	X	X	X	X
Photography of Treatment Area(s) – prior to treatment	X (baseline)	X	X	X	X	X	X	X
Photography of Treatment Area(s) – After treatment			X					
Investigational/Comparator Device Treatment	X	X	X	X	X			
Subject experience and satisfaction questionnaire	X		X*	X*	X*	X*		X

Procedure	Visit 1	Visit 2	Visit 3	Visit 4	Visit 5	Visit 6	Visit 7	Visit 8
	Treatment 1 ^c	Treatment 2	Treatment 3	Treatment 4 Optional	Treatment 5 Optional	1 month Follow-up 1	3 months Follow-up 2	6 months Follow-up 3
GAIS Assessment		X	X	X	X	X	X	X
FWCS Assessment	X _f	X	X	X	X	X	X	X _f
WAS Assessment	X _f	X	X	X	X	X	X	X _f
Subject VAS Pain assessment	X	X	X	X	X			
Subject Assessment Questionnaire (regarding downtime, skin erythema, redness and scabs)		X	X	X	X	X		
Adverse Events	X	X	X	X	X	X	X	X
Subject Compliance	X	X	X	X	X	X	X	X
Post Treatment Care Instructions	X	X	X	X	X			

- A limited physical examination will be performed at Screening to support the eligibility determination. System review will include general appearance, and a routine physical examination, according to the standard of care and as customary for fractional treatments.
- At Screening, the review of concomitant medications should include those taken within the past year.
- All assessments on treatment days are to be performed prior to treatment; the assessments performed prior to Treatment 1 will be designated as Baseline.
- Treatment sessions 4 & 5 are optional for both treatment options, based on the investigator's assessment of the subject's response.

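### The paired baseline-to-last-follow-up test in section 11.3 cannot be run for GAIS, VAS pain or the downtime/redness questionnaire, because the flowchart schedules no such pair for them

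*Combined protocol and SAP*

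**What the plan says.** Section 11.3 opens with a rule for the whole list of secondary endpoints: "All parameters below will be summarized at baseline condition and all post-baseline conditions". It then names the test: "The change from baseline to the last follow-up will be analyzed using Wilcoxon paired test". No endpoint is exempted. The list (11.3.1.1 to 11.3.1.8) comprises FWCS, GAIS, WAS, Subject Experience, VAS pain, downtime, a redness/edema/crust questionnaire and End-User Experience. The section also promises descriptive output: "The following secondary endpoints will be summarized in appropriate tables by device and visit".

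Section 11.3.1.9 adds repeated measures or Friedman tests within device, and a two-sample t-test or Mann-Whitney test of the changes between devices.

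The section 9 flowchart has eight visits: Visits 1-5 are Treatments 1-5 (4 and 5 optional), and Visits 6-8 are the 1-, 3- and 6-month follow-ups. A footnote puts all treatment-day assessments before treatment and defines baseline as those made before Treatment 1. The relevant rows are "GAIS Assessment", "Subject VAS Pain assessment", "Subject experience and satisfaction questionnaire" and the recovery form, which begins "Subject Assessment Questionnaire (regarding downtime, skin erythema, redness and scabs".

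**The concern.** A paired test of change needs a baseline value and a last-follow-up value on the same scale from the same subject. The rule suits a wrinkle score measured at every visit. It does not suit a score that is already an improvement rating, pain from a procedure, or recovery after a session.

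Two things are at stake. First, a named test has no data for several endpoints, so the analyst must drop or replace it, possibly after seeing the results. Second, the between-device comparison is worded in terms of changes. For pain and recovery the useful question is which device hurts more or heals more slowly, and that is a difference in level. The protocol gives patient comfort as one reason for the device's design, and pain and downtime are listed endpoints that bear on it.

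**Working it through.** The plan gives no figure on this point, so the check sets the rule in section 11.3 against the flowchart rows in section 9. Each row has eight cells, so the columns align with the visits. Baseline is Visit 1 and the last follow-up is Visit 8. A looser check allows Visit 1 with any of Visits 6, 7 or 8.

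| Assessment | Visits marked | Visit 1 and Visit 8? | Visit 1 and any of 6-8? |
|---|---|---|---|
| FWCS | 1-8 | yes | yes |
| WAS | 1-8 | yes | yes |
| Subject experience | 1, one of 3-6, 8 | yes | yes |
| GAIS | 2-8 | no: no baseline | no |
| VAS pain | 1-5 | no: no follow-up | no |
| Downtime/erythema/redness/scabs | 2-6 | no: neither | no |

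The looser reading rescues none of the last three. A pair arises for pain only if a treatment visit is counted as a follow-up, which the column labels do not support. If the Visit 1 pain score describes pain from Treatment 1, it is not a baseline under the footnote's definition either.

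Count over the eight listed endpoints:
- 2 fit the rule (FWCS, WAS).
- 1 has the pair, but the change is meaningful only for items that make sense before treatment (Subject Experience; a satisfaction item has no clear pre-treatment value).
- 3 have no pair (GAIS, VAS pain, downtime).
- 1 has no pair if the flowchart's recovery form also supplies it (11.3.1.7).
- 1 has no flowchart row (End-User Experience).

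Total: 2 + 1 + 3 + 1 + 1 = 8.

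Why a change is the wrong quantity for pain and recovery: write the expected score on device d at session k as L(d) + s(k), where L is the device's level and s a session effect common to both devices. The change from session 1 to session k is [L(d) + s(k)] - [L(d) + s(1)] = s(k) - s(1). The device level cancels. Two devices with very different pain levels would then show the same expected change, and the test in 11.3.1.9 would see no difference. A non-zero result would show that pain drifts differently over sessions, not that one device hurts more. Because sessions 4 and 5 are optional, the last session of such a change would also differ between subjects.

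GAIS does not have this difficulty. It is already an improvement score, so its observed value can be compared between devices directly.

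**The case against.** The strongest reply is that these endpoints are not left without an analysis. The changes in 11.3.1.9 are not tied to baseline and last follow-up. They can be computed across the scheduled visits for pain (1-5) and for the questionnaire (2-6), Friedman tests can run within device, and tables by device and visit are promised. This stands. A reader might infer that the between-device quantity for pain and recovery is undefined. The documents do not support that: it is imprecise and unsuitable, but it can be computed.

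Three further inferences are tempting and also go too far:
- **Pain is captured for at most 2 of 3 sessions in a three-session subject.** This requires the pre-treatment footnote to apply literally to VAS. The pain row is marked at exactly the visits where the device is applied, so the natural reading is one score per treatment session. The row "Photography of Treatment Area(s) – After treatment" also suggests that the footnote was not meant without exception. What remains is a wording conflict to reconcile.
- **Visit 6 recovery forms mix sessions 3, 4 and 5.** This assumes that untreated optional visits are skipped and that each form covers only the latest session. The form is not in the documents. Even on those assumptions, Visit 6 has one coherent meaning: recovery after the last session.
- **End-User Experience and 11.3.1.7 are unscheduled.** The flowchart lists subject-visit procedures, and an operator's assessment would not need a row there. By content, the recovery form appears to cover 11.3.1.7, although the names differ. These are missing details, not contradictions.

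It is also fair to say that comfort is design background. The stated objective is safety and performance, the trial is sized on FWCS, and no success criterion depends on pain or downtime. That limits the importance of the point. It does not give the paired test any data.

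**Conclusion.** The point holds for GAIS, VAS pain and the downtime/erythema/redness/scabs questionnaire. Section 11.3 states a rule without exception, and the flowchart contradicts it, so this is more than missing detail. By name, 3 of the 8 listed secondary endpoints are affected, or 4 if the same questionnaire supplies 11.3.1.7. For pain and recovery, the fallback comparison of changes does not address the difference in level between devices. For GAIS, only the wording of the within-arm test and the choice of visit need attention.

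This rests on the flowchart as printed, on baseline meaning Visit 1, and on follow-up meaning Visits 6-8. The argument about change versus level does not depend on how the pain footnote is resolved. Sample size, power and the primary FWCS analysis are unaffected. Skin examination and adverse events are recorded at every visit, so safety monitoring does not depend on these endpoints. The plan should be corrected, but the correction is small.

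**What to change.** In section 11.3:
- Restrict the baseline-to-last-follow-up change analysis to FWCS and WAS, and to Subject Experience items that have a meaningful pre-treatment value.
- Compare GAIS between devices on the observed score at Visit 8, by Mann-Whitney.
- Compare VAS pain and downtime/time to resolution between devices on one observed value per subject, by Mann-Whitney. The mean over the non-optional sessions 1-3 is one suitable choice. The documents do not require that summary, and another could serve if it is fixed in advance and does not depend on whether the optional sessions were given.

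In section 9, reconcile the footnote that places all treatment-day assessments before treatment with the VAS pain row. A summary by session also needs a sentence saying which session each pain score and each recovery form describes. It would help to name the form that supplies 11.3.1.7 and to say when End-User Experience is recorded, but the point does not depend on either.

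The cost is minor SAP rewording and one flowchart footnote; the proposed comparisons use data already scheduled. The downside is that no change-from-baseline test is reported for GAIS, pain or recovery. Little is lost, since the schedule cannot supply one.
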